### **Clinical Global Impression (CGI)**

The CGI (22) is the general name for 2 scales, the CGI-Severity scale (CGI-S) and the CGI-Change scale (CGI-C). The CGI-S scale measures global severity of illness at a given point in time. It will be rated on a 7-point Likert-type scale ranging from 1 (normal, not ill at all) to 7 (extremely severe). The CGI-S will be assessed at all visits, starting at baseline. The CGI-C scale will measure the change in the patient's clinical status from baseline using a 7-point scale, ranging from 1 (very much improved) to 7 (very much worse), with a score of 4 indicating no change. The change from the patient's baseline condition will be assessed by the Investigator at all post-baseline visits. In completing the CGI-C, the rater will review all efficacy-related data, and assess its clinical meaningfulness.

### **Parkinson's Disease Questionnaire-39 items (PDQ-39)**

The PDQ-39 (23) comprises 39 questions measuring eight dimensions of health: mobility, activities of daily living, emotional well-being, stigma, social support, cognition, communication and bodily pain. Dimension scores are coded on a scale of 0 (perfect health as assessed by the measure) to 100 (worst health as assessed by the measure). A summary index score could also be calculated. The contents of the instrument were developed on the basis of exploratory in-depth interviews with patients with Parkinson's disease, and the reliability, validity, and sensitivity to change of the instrument were then assessed in a number of large scale surveys.

### **Numerical Rating Scale (NRS)**

The NRS (24) is a segmented numeric version of the visual analogue scale (VAS) in which a patient selects a whole number that best reflects the intensity of his/her pain, ranging from '0' ("no pain") to '10' ("worst possible pain").

Patients should record the intensity of their PD-associated pain, as the worst pain experienced over the past 24 hours (at any time during the day), in the evening before going to sleep.

If the patient suffered from more than one PD-associated pain, the more severe pain will be documented.

### 10.1.7 Safety Evaluations

Safety will be assessed throughout the study, i.e. from the provision of informed consent until the last patient visit. In addition, any AE that, in the opinion of the Investigator, requires the patient to withdraw from treatment or from the study, will be followed until the event has subsided or the condition has stabilised. All SAEs that are spontaneously reported within 30 days of a patient's last dose of study drug will also be reported and followed.

Individual safety assessments will be performed using the parameters and time points for collection listed below:

- Physical examination, clinical chemistry and haematology and 12-lead ECG at screening (visit 1) and week 16 (visit 6/EOT/ET).
- Neurological examination at screening (visit 1).
- Vital signs at each study visit AEs at every post-screening visit.

Further details are provided in [Section 10.1](#) and in the Study Flow Chart ([Section 29.0, Appendix 1](#)).

Further information regarding AE definitions and reporting is provided in [Section 17.0](#).

## 10.2 Compliance

The prescribed dosage, timing and mode of administration of study medication may not be changed. Study medication accountability and patient compliance will be documented throughout the treatment period using study-specific study medication dispensing and return record forms.

The evaluation of compliance will be done using the following formula:

$$\% \text{ of administered drug} = 100 \times \frac{\text{Total number of administered doses}}{\text{Total number of scheduled doses}^*}$$

*\*1 dose x number of days between visits*

Patients will be asked to return all unused medication. From visits 3 to 6 (weeks 2 to 16), the study medication dispensed at the previous visit will be retrieved by the Investigator and compliance assessed by tablet count.

Non-compliance is defined as taking less than 80% or more than 120% of study medication during any visit-to-visit evaluation period.

Patients exhibiting non-compliance as assessed by tablet counts should be counselled on the importance of good compliance to the study dosing regimen.

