### 9.2.1 Visit 2 - Baseline Visit (Week 0 / Day 1)

The following assessments and procedures will be performed as detailed in the Study Flow Chart ([Section 29.0, Appendix 1](#)):

- Check of inclusion and exclusion criteria (note: inclusion and exclusion criteria must be fulfilled before patient is randomized).
- Vital signs (pulse rate, systolic and diastolic blood pressure measured after at least 5 minutes in the supine position).
- Completion of UPDRS, PDQ-39 and CGI-S by the rater ([Section 10.1.6](#)).
- Completion of NRS by the patient (the night before the visit) ([Section 10.1.6](#)).
- Recording of prior medications, concomitant medications and therapies.
- Recording of AEs ([Section 17.0](#)).
- Review and evaluate daily diary ([Section 10.1.6](#)).
- Provide additional daily diary training, as required.
- Issue daily diary with instructions to be completed two days before the visit at week 2 (visit 3).
- Randomisation to study treatment.
- Following completion of the relevant assessments and procedures, patients will take their first 50 mg dose of oral safinamide or placebo at the study center.
- Dispense study medication (safinamide or placebo 50 mg od) for the next 14 days. Patients will take 50 mg/day safinamide at home in the morning for 2 weeks, then the dose will be increased at home to 100 mg/day the day after the Visit 3/week2, ideally at day 15. Safinamide can be taken with or without food.

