### 9.2.2 Visit 3 (Week 2 / Day 14 ± 3 days), Visit 4 (Week 6 / Day 42 ± 3 days) and Visit 5 (Week 10 / Day 70 ± 3 days)

At weeks 2, 6 and 10 (visits 3, 4 and 5), the following assessments and procedures will be performed as indicated in the Study Flow Chart ([Section 29.0, Appendix 1](#)):

- Vital signs (pulse rate, systolic and diastolic blood pressure measured after at least 5 minutes in the supine position).
- Completion of UPDRS, PDQ-39, CGI-S and GCI-C by the rater.
- Completion of NRS by the patient (the night before the visit).
- Recording of concomitant medications and therapies.
- Recording of AEs.
- Review and evaluate daily diary.

- Provide additional daily diary training, as required.
- Issue daily diary at weeks 2, 6 and 10, with instructions to be completed two days before the next visit (weeks 6, 10 and 16).
- Drug accountability.
- Dispense study medication (safinamide or placebo 50 and 100 mg od). Patients will take 100 mg/day safinamide at home in the morning for 14 weeks. In the case of intolerable dopaminergic adverse events (AEs), e.g. dyskinesia, it is suggested to decrease the dose of L-dopa by a telephone call as a first step and consider the decrease of the dose of safinamide or placebo from 100 to 50 mg od as a second step. In this second case, patients should undergo an unscheduled visit for safety reasons and maintain the 50 mg dose for the rest of the study. Patients who do not tolerate the 50 mg dose should withdraw from the study and complete the early termination visit assessments, when possible.

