## 9.4 Unscheduled Visit

An unscheduled visit should be performed in case of down-titration of safinamide or placebo from 100 to 50 mg for safety reasons. The following assessments and procedures will be performed as detailed in the Study Flow Chart ([Section 29.0, Appendix 1](#)):

- Physical examination including body weight.
- Vital signs (pulse rate, systolic and diastolic blood pressure measured after at least 5 minutes in the supine position).
- 12-lead ECG in the supine position.
- Recording of concomitant medications and therapies.
- Drug accountability and drug dispensing.
- Recording of AEs.

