**TABLE 3 DESCRIPTION OF INVESTIGATIONAL MEDICINAL PRODUCT (SAFINAMIDE)**

| Characteristic  | Investigational Product                                |
|---|--|
| Product name  | Safinamide   |
| Active ingredient   | Safinamide methanesulfonate                            |
| Physical appearance   | Orange to copper, round, biconcave film-coated tablets |
| Dosage  | Once daily   |
| Unit dose strength  | 50 mg, 100 mg safinamide (free base)                   |
| Route of administration                                       | Oral   |
| Treatment duration  | 16 weeks   |
| Manufacturer                                      | Zambon S.p.A. Vicenza                                  |
| Company performing primary packaging                          | Zambon S.p.A. Vicenza                                  |
| Company performing secondary packaging/labelling  | Parexel  |

 Manufactured according to current Good Manufacturing Practice.

 Labelling will conform to applicable regulatory requirements.

Each tablet consists of safinamide methanesulfonate combined with the following inactive ingredients: microcrystalline cellulose, crospovidone, colloidal silicone dioxide, magnesium stearate, and for the coating: purified water, hypromellose and polyethylene glycol. Candurin® pigments are included for colour modification.

Safinamide film-coated tablets, 50 and 100 mg, will be supplied in PVC/PVDC60/AI blisters.

A sufficient quantity of safinamide film-coated tablets (50 mg and 100 mg) will be supplied by the Sponsor, together with certificates of analysis, material safety data sheets, expiry dates and a statement that the study medication has been manufactured in accordance with GMP.

Placebo film-coated tablets are composed of the inactive ingredients used in the safinamide tablets (microcrystalline cellulose, crospovidone, colloidal silicone dioxide, magnesium stearate, and for the coating: purified water, hypromellose and polyethylene glycol). Candurin® pigments are included for colour modification. A description of placebo is given in [Table 4](#).

Placebo film-coated tablets, 50 and 100 mg, will be supplied in PVC/PVDC60/AI blisters.

A sufficient quantity of placebo film-coated tablets (50 mg and 100 mg) will be supplied by the Sponsor, together with certificates of analysis, material safety data sheets, expiry dates and a statement that the study medication has been manufactured in accordance with GMP.

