## **12.2 Investigational Medicinal Product Dispensing and Administration**

The first dose of safinamide or placebo (50 mg) will be administered at the study centre following completion of all baseline assessments and based on randomization list. Patients will take subsequently 50 mg od safinamide (or placebo) at home (i.e. either unsupervised or with the assistance of a caregiver) in the morning (at breakfast time, in addition to the morning dose of L-dopa and other, if any, PD medications) for 2 weeks and increase then the dose to 100 mg/day the day after the Visit 3/week 2, ideally at day 15 (at home).

Treatment with oral safinamide (or placebo) 100 mg od will continue up to week 16 and will be self-administered (i.e. either unsupervised at home or with the assistance of a caregiver) at approximately the same time each day. On study visits after visit 2, patients should take their dose of safinamide/placebo in the morning prior to attending the study centre.

Patients will be asked to return all unused medication to the study centre for compliance calculation ([Section 10.2](#)).

*Throughout the study, patients will continue to take their standard, prescribed anti-Parkinsonian treatment; doses must be kept constant.*

*In the case of intolerable dopaminergic adverse events (AEs), e.g. dyskinesia, it is suggested to decrease the dose of L-dopa by a telephone call as a first step and consider the decrease of the dose of safinamide or placebo from 100 to 50 mg od as a second step. In this second case, patients should undergo an unscheduled visit for safety reasons and maintain the 50 mg dose for the rest of the study. Patients who do not tolerate the 50 mg*

dose should withdraw from the study and complete the early termination visit assessments, when possible.

The patients will be provided at each visit with sufficient IMP for the treatment until the following visit, including additional spare tablets.

Study medication will be stored on-site in accordance with the label requirements in a secure area with access limited to the Investigator and authorised study personnel.

No special procedures for the storage or the safe handling of the study medication are required. The Sponsor and their authorised representatives such as study monitors or auditors as well as regulatory inspectors will be permitted, upon request, to audit the supplies, storage and dispensing procedures and records in accordance with applicable regulatory requirements.

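### The Section 10.2 compliance formula, read literally, is one dose short from Visit 2 to Visit 3 and takes no account of tablet strength, so some patients near the limits are misclassified

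*Protocol*

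**What the plan says.** Section 10.2 defines compliance as 100 times the doses administered divided by the doses scheduled, with scheduled doses given by "1 dose x number of days between visits". Unused medication is returned at Visits 3 to 6 and "compliance assessed by tablet count". The limits are explicit: "Non-compliance is defined as taking less than 80% or more than 120% of study medication during any visit-to-visit evaluation period". Strength is not mentioned. The section also opens by ruling out any change to the prescribed dosage.

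Three other places fix which doses fall in each interval and which tablets the patient holds:

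- Section 9.2.1 (Visit 2, Day 1): "patients will take their first 50 mg dose of oral safinamide or placebo at the study center".
- Section 12.2: "On study visits after visit 2, patients should take their dose of safinamide/placebo in the morning prior to attending the study centre".
- Section 9.2.2 (Visits 3 to 5): "Dispense study medication (safinamide or placebo 50 and 100 mg od"). The same bullet has patients on 100 mg daily for 14 weeks and allows a reduction to 50 mg for intolerable dopaminergic events.

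Section 9.4 covers the unscheduled visit for such a reduction and lists "Drug accountability and drug dispensing". Table 3 gives one appearance for both strengths: "Orange to copper, round, biconcave film-coated tablets".

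Section 20.4.2 puts two conditions on the PP set: compliance with study drug, and no major deviation likely to affect efficacy.

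**The concern.** The protocol fixes this formula itself, so it should return 100% for a patient who takes every dose and should place patients correctly against its own limits. In the first interval it appears to do neither, because the dosing days include both visit days while the denominator is the difference between them.

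Separately, the dose changes at Visit 3 and may later be reduced, but the score counts tablets only. It cannot tell a patient taking the assigned strength from one taking the other strength once a day. Section 10.2 also does not say what the scheduled dose is after a reduction that other sections allow.

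At stake are who is counselled for non-compliance and, if the PP set uses these limits, who is in the set that Section 20.4.3 compares with the FAS to judge the effect of deviations and dropouts.

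**Working it through.** **Inputs.** Nominal visit days are 1, 14, 42, 70 and 112, with a window of ±3 days at Visit 3 (Sections 9.2.1 to 9.2.3 and the flow chart). Dosing is once daily. The Day 1 dose is taken at the site, and on later visit days the dose is taken before the visit. The limits are 80% and 120%.

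**Stated treatment length.** 16 weeks × 7 = 112 daily doses. Counting from the dosing instructions:

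- Visit 2 to 3: Days 1 to 14 = 14 doses
- Visit 3 to 4: Days 15 to 42 = 28
- Visit 4 to 5: Days 43 to 70 = 28
- Visit 5 to 6: Days 71 to 112 = 42
- Total 14 + 28 + 28 + 42 = 112, which reproduces the 16 weeks.

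**Section 10.2 denominators.** (14 − 1) + (42 − 14) + (70 − 42) + (112 − 70) = 13 + 28 + 28 + 42 = 111. Only the first interval is short, by one dose. Later intervals are exact whatever the visit window, because each contains its closing visit day and not its opening one.

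**Effect in the first interval.** With Visit 3 on Day V, V doses are due and the formula divides by V − 1. The table lists every dose count whose classification changes, as true percentage → scored percentage.

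| Visit 3 day | Due | Denominator | Full intake scores | Below 80%, scored compliant | Within limits, scored above 120% |
|---|---|---|---|---|---|
| 11 | 11 | 10 | 110.0% | 8 doses: 72.7 → 80.0 | 13: 118.2 → 130.0 |
| 12 | 12 | 11 | 109.1% | 9: 75.0 → 81.8 | 14: 116.7 → 127.3 |
| 13 | 13 | 12 | 108.3% | 10: 76.9 → 83.3 | 15: 115.4 → 125.0 |
| 14 | 14 | 13 | 107.7% | 11: 78.6 → 84.6 | 16: 114.3 → 123.1 |
| 15 | 15 | 14 | 107.1% | none | 17: 113.3 → 121.4; 18: 120.0 → 128.6 |
| 16 | 16 | 15 | 106.7% | 12: 75.0 → 80.0 | 19: 118.8 → 126.7 |
| 17 | 17 | 16 | 106.25% | 13: 76.5 → 81.25 | 20: 117.6 → 125.0 |

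So one low count is wrongly passed on six of the seven days, and one or two high counts are wrongly failed on all seven. A patient with 11 of 14 doses and full intake afterwards has taken (11 + 98)/112 = 97.3% of all doses.

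**If the Day 1 site dose is left out of the count.** Days 2 to 14 are 13 doses over 13 days, and the first interval is exact.

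**Strength, Visit 3 to 4 (28 days, 100 mg assigned, 28 × 100 = 2,800 mg).**

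- One 50 mg tablet daily: 28/28 = 100% by count; 1,400/2,800 = 50% by mg.
- 50 mg on 14 days and 100 mg on 14 days: 100% by count; (700 + 1,400)/2,800 = 75% by mg.
- One tablet of each strength daily: 56/28 = 200% by count, which is flagged.

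Substituting one strength for the other is therefore not detected, while taking both is.

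**The case against.** A reader might infer that patients on the wrong dose, or below 80%, are admitted to the PP set. The documents do not support this. Section 20.4.2 has a separate major-deviation condition and gives, as a possible example, study drug not given as the protocol sets out. Exclusions are decided jointly before unblinding. The examples are only possible ones, so exclusion is not assured, but a good compliance score does not secure entry. Section 20.4.2 also does not cite the 80–120% limits; the only consequence that Section 10.2 attaches to them is counselling.

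A reader might also take the formula to be simply lenient. It is not: it fails some patients who are within limits.

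The undercount depends on the Day 1 dose being in the numerator. Section 9.2.1 lists the site dose before the dispensing of the take-home supply, and Section 10.2 counts medication dispensed at the previous visit, so a home-only count is arguable. Against that, the numerator is all administered doses, with no exclusion. At best the text is ambiguous.

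On strength, the wording in Section 9.2.2 need not mean that every patient takes both home. One bullet covers three visits and also patients already reduced to 50 mg, so it may list the strengths in use; dispensing at the Section 9.4 visit fits that reading. Table 3 gives colour and shape and does not say the strengths cannot be told apart. Returned tablets and the Section 12.4 log, which records quantity and description, could expose a substitution. These points stand, but they rest on records outside the formula; the score itself would still be 100%.

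Finer derivation rules may sit in the SAP. The denominator and limits, however, are stated here.

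**Conclusion.** A minor defect, wrong as written. On its literal reading Section 10.2 schedules 111 doses where the protocol's own instructions give 112. The whole error lies in the 50 mg interval, and it misclassifies at most one low and one or two high dose counts per Visit 3 day. This assumes that the Day 1 site dose is counted as administered; without it the first interval is correct.

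The tablet count does not register strength, so patients who substitute 50 mg for an assigned 100 mg tablet meet the compliance condition at 100%. They may still be removed from the PP set as major deviations.

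The consequence is confined to compliance scoring and counselling and, if the PP set uses this rule, to marginal membership of a supportive set. How many patients would be affected cannot be derived from the protocol. The FAS, and with it the primary analysis, is unaffected.

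**What to change.** In Section 10.2:

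- Count tablets of the strength assigned on each day against the number scheduled at that strength, splitting the interval at the date of any permitted dose change.
- Say whether the Day 1 site dose is counted. Either set the Visit 2 to Visit 3 denominator to days between visits plus one (full intake 14/14), or keep the denominator and leave the site dose out of the numerator (13/13). With Visit 3 on Day 14, both correct the examples above: 11 doses in all score 11/14 = 78.6% or 10/13 = 76.9%, and 16 score 16/14 = 114.3% or 15/13 = 115.4%.

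Reconcile Section 9.2.2 with Section 9.4 on which strengths are dispensed at Visits 3 to 5. Reconcile the opening of Section 10.2, which bars dosage changes, with the down-titration text in Sections 9.2.2, 11.2 and 12.2. Which dose rule applies is for the sponsor to settle.

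The cost is a few sentences in Section 10.2, a clarification in Section 9.2.2 and a change to the derivation program. The accountability records in Sections 10.2 and 12.4 should supply the counts, provided returns are logged by strength.

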## 10.3 Pharmacodynamics

Not applicable.

## 10.4 Pharmacokinetics

Not applicable.

## 11.0 CONCOMITANT TREATMENTS

Concomitant medication is defined as any medication, other than the study medication, which is taken during the study from the time the patient provides informed consent until the last study visit for the patient, including prescription and over-the-counter medicines. All concomitant medications taken should be recorded on the eCRF.

### 11.1 Excluded Medications

Medications that are excluded prior to the study are listed in the exclusion criteria ([Section 8.2.2](#)).

Selective serotonin reuptake inhibitors (SSRIs) other than fluoxetine or fluvoxamine, selective serotonin-norepinephrine reuptake inhibitors (SNRIs), tricyclic and tetracyclic antidepressants can be administered provided they remain at the lowest effective dose and remain stable throughout the study.

Dextromethorphan, sympathomimetics, nasal and oral decongestants or cold medicinal products containing ephedrine, pseudoephedrine, phenylephrine or phenylpropanolamine are permitted if used for treating cough but must be used with caution.

Concomitant medications that are considered necessary for the safety and well-being of the patient are permitted during the study at the discretion of the Investigator, with the following exceptions:

- Opioids and opiates
- L-dopa infusion and MAOIs
- Fluoxetine or fluvoxamine
- Pethidine
- Any other investigational agent
- Traditional Chinese medicine related to nervous system disease
- Acupuncture for treatment IPD

The use of any prohibited concomitant medication is a protocol deviation and should be recorded as such within the eCRF.

In addition, patients must not participate in any other clinical study of an investigational product or device whilst participating in this study.

### 11.2 Permitted Medications

Prior and concomitant medications which are considered necessary for the safety and well-being of the patient are permitted during the study at the discretion of the Investigator provided the medication is not listed within the Exclusion Criteria ([Section 8.2.2](#)) or in the Excluded Medications ([Section 11.1](#)).

The dose of L-dopa and/or of the concomitant anti-Parkinson treatments must be kept constant throughout the study.

In the case of intolerable dopaminergic adverse events (AEs), e.g. dyskinesia, it is suggested to decrease the dose of L-dopa by a telephone call as a first step and consider the decrease of the dose of safinamide or placebo from 100 to 50 mg od as a second step.

In this second case, patients should undergo an unscheduled visit for safety reasons and maintain the 50 mg dose for the rest of the study. Patients who do not tolerate the 50 mg dose should withdraw from the study and complete the early termination visit assessments, when possible.

